informed signed consent or assent will be obtained from all participants. Refusal to participate will in no way influence the subjects' relationship with the physicians, nurses or researchers, or with Yale University or Yale-New Haven Hospital, nor will it influence their receipt of treatment. An opportunity will be given to the parent/subject to indicate if the genetic sample results can be used for recruitment for current and future studies. Once a participant turns 18, if he/she has not completed the study, will be reconsented in order to complete the study.

6. Subject Population: Provide a detailed description of the types of human subjects who will be recruited into this study.

We will enroll an equal number of 100 obese and 100 lean, between the age of 15 and 25, lean (BMI <85th percentile) and obese (BMI > 95th percentile). The two groups will be matched by age, gender, pubertal stage and ethnicity. As controls we will recruit only lean adolescents at risk of developing obesity, prediabetes or diabetes due to their family history.

7. Subject classification: Check off all classifications of subjects that will be specifically recruited for enrollment in the research project. Will subjects who may require additional safeguards or other considerations be enrolled in the study? If so, identify the population of subjects requiring special safeguards and provide a justification for their involvement.

 Children	 Healthy	 Fetal material, placenta, or dead fetus
 Non-English Speaking	 Prisoners	 Economically disadvantaged persons
 Decisionally Impaired	 Employees	 Pregnant women and/or fetuses
 Yale Students	 Females of childbearing potential	

NOTE: Is this research proposal designed to enroll children who are wards of the state as potential subjects?

Yes No X

8. Inclusion/Exclusion Criteria: What are the criteria used to determine subject inclusion or exclusion?

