Inclusion criteria: Good general health, taking no medication on a chronic basis, age 15 to 25 years, in puberty (girls and boys: Tanner stage III – V), BMI >25th and <85th for lean cohort; BMI >95th for obese cohort, girls who begin menstruating must have a negative pregnancy test during the study. Exclusion criteria: hematocrit below 32%, baseline creatinine >1.0 mg, food allergies, pregnancy, presence of endocrinopathies (e.g. Cushing syndrome), significant chronic illness.

The hematocrit will be measured in all the patients at the research unit the day of the visit before the beginning of the study. During the assessment of vital signs the patients will be asked about signs of anemia (fatigue, malaise, weakness, dizziness). The study will be performed only if the hematocrit is above 32% and the patients does not refer any symptoms of anemia. The hematocrit will be measured using the hematocrit analyzer available at the research unit (HemataSTAT II Analyzer Serial).

9. How will eligibility be determined, and by whom?

Before the enrollment, the clinical characteristics will be assessed through a clinical evaluation during a screening visit in which the PI and the study coordinator will assess the eligibility through a comprehensive evaluation (height, weight, disease history, current medications etc.).

10. Risks: Describe the reasonably foreseeable risks, including risks to subject privacy, discomforts, or inconveniences associated with subjects participating in the research.

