V2012 (Kayesville, UT) in order to enroll a sufficient number of obese children to detect differences in SCFA synthesis for aim 3. Based on this sample size, the number of lean children was then determined to detect differences between lean and obese (aim 1). For aim 1, given a standard deviation of 1.0 for SCFA, 100 lean children (compared to 100 obese children) will be required to detect a difference of 0.65 with 90% power at the two-sided 0.05 significance level. This sample size will also provide 80% power to detect an rsquare of 0.07 (aim 2). Statistical analyses: Analysis for Aim 1: the primary outcome will be the peak percent change from fasting in total SCFA estimated by dividing the difference between total SCFA at fasting and the peak total SCFA by the total SCFA at fasting. Total SCFA is calculated by summing the synthetic rates of the single SCFAs. Peak percent change will be compared between the lean and obese groups using a mixed model to account for the pair matching. A fixed effect will be included for group (obese/lean) and a random effect for an indicator of the matched pair. Differences in means along with 95% confidence intervals will be estimated. We will also explore between group differences in SCFA across all post-inulin time-points by estimating the area under the curve following inulin. Since the pre-intervention diet will be based on the subjects' usual intake, we will adjust for dietary intake to try to overcome the possibility that dietary patterns during the study might affect SCFA synthesis. Since the two groups will be matched by age, gender, Tanner stage and ethnicity the analyses will not need to be adjusted for these variables. Nevertheless, we will determine whether differences between lean and obese groups are modified by gender by adding an interaction of gender by group. Analysis for Aim 2: To evaluate the association between total SCFA and de novo lipogenesis, peak percent changes in de novo lipogenesis will be regressed on peak percent changes in total SCFA using a mixed model. The mixed model will include a fixed effect for peak percent total SCFA and a random effect for the matched pair indicator. To explore whether the magnitude of the associations may be dependent on other variables (such as gender), interactions between percent peak total SCFA and these variables will be included to the models in order to describe the degree of effect modification. An additional exploratory analysis using a doubly multivariate repeated measures mixed model will be evaluated to examine the correlation of total SCFA and de novo lipogenesis across all post-inulin time-points.

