
Statistical Plan for Aim 3. Justification of Sample size: In our preliminary data from obese children we observed a standard deviation for percent peak total SCFA synthesis of 1.0 and an absolute difference of 1.5% between those with the lowest and highest BMI. Given the following: 1) a power of 90%, 2) a standard deviation of 1.0, and 3) a two-sided 0.05 significance level a sample size of 21 obese children receiving both low CHO vs control diet will be required to detect a difference of 0.75 in peak total SCFA synthesis. The conservative 0.75 difference was selected based on being 50% of that estimated between the highest and lowest BMI in our preliminary work. We'll enroll 26 obese children for aim 3 to accommodate up to a 20% dropout. Statistical Analyses: The primary objective of the analysis is to demonstrate that a low CHO diet will lower SCFA synthetic rate more than control at follow-up. The percent change in peak total SCFA rate, calculated as the follow-up peak total SCFA minus the baseline peak total SCFA divided by the baseline peak total SCFA, will be compared between the low CHO period and the control period using a repeated measures mixed model. The mixed model will include fixed effects for treatment and period as well as the baseline covariates of SCFA, age, sex, pubertal stage and ethnicity. A random effect will be included for subject to allow for correlation between repeated measures. The treatment by period interaction will be evaluated and if significant ($p < 0.10$) examination of the primary aim will focus on the interventions received during the first period (i.e. to exclude the possibility of carryover). Linear contrasts and two-sided 95% confidence intervals will be estimated comparing mean percent peak total SCFA change for low CHO to control. Sex-specific effects of low CHO will be assessed by inclusion of interactions of treatment with sex. Given the assumption required for missing data, we will evaluate patterns of missing data as well as determine baseline characteristics that are predictive of dropout. If identified, these characteristics will be included as covariates in supportive sensitivity analysis.

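### Aim 2's slope model leaves out age, sex, pubertal stage, ethnicity and obese/lean group; the random pair effect removes only part of any confounding by the matched factors

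*Combined protocol and SAP*

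**What the plan says.** All references are to Section I unless noted.

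- **Outcome and exposure (item 13, Analysis for Aim 2).** "peak percent changes in de novo lipogenesis will be regressed on peak percent changes in total SCFA using a mixed model". The exposure is measured and continuous.
- **Model terms (same paragraph).** "The mixed model will include a fixed effect for peak percent total SCFA and a random effect for the matched pair indicator". No other fixed effect is listed.
- **Other variables in Aim 2.** They appear only in exploratory work: "interactions between percent peak total SCFA and these variables will be included to the models in order to describe the degree of effect modification". Gender is the only one named.
- **What is matched (item 6, Subject Population).** "The two groups will be matched by age, gender, pubertal stage and ethnicity". The groups are lean and obese.
- **Reason for not adjusting (item 13, Analysis for Aim 1).** "Since the two groups will be matched by age, gender, Tanner stage and ethnicity the analyses will not need to be adjusted for these variables". This sentence stands in the Aim 1 paragraph.
- **Spread of the matched factors (item 8).** Eligible subjects are "age 15 to 25 years, in puberty", with Tanner stage III to V.
- **For comparison, Aim 3.** That model has "fixed effects for treatment and period as well as the baseline covariates of SCFA, age, sex, pubertal stage and ethnicity".

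**The concern.** In Aim 1 the exposure is obese versus lean, which is the factor the pairs are matched across, so leaving the matching variables out of the mean comparison can be defended. In Aim 2 the exposure is the SCFA response, and nobody matched on that. The members of a pair share age, sex, pubertal stage and ethnicity, but pairs differ from one another on all four. If older pairs, say, had both larger SCFA responses and larger lipogenesis responses, the two would rise together across pairs without either driving the other.

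The random pair intercept looks as if it deals with this. It would do so fully only if the slope came entirely from differences inside pairs. A random intercept also uses the differences between pairs, and these remain confounded.

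Aim 2 asks whether SCFA synthesis enhances hepatic lipogenesis. A slope produced by shared demographic or pubertal factors would be read as support for that, and factors acting in opposite directions could hide a real association.

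**Working it through.** **1. The plan's own Aim 2 figure.** Item 13 gives 80% power for an R-square of 0.07 with 100 lean and 100 obese subjects. For one predictor, the noncentral F test has λ = n·R²/(1 − R²). With n = 200, λ = 200 × 0.07/0.93 = 15.1 and power is 97.1% (two-sided 0.05 assumed; alpha is not restated for Aim 2). The stated 80% corresponds to n = 107, and n = 100 gives 77.5%. So the figure is not reproduced at 200. That is a separate matter, but it shows that a few extra model terms are affordable. The design effect is a standardised slope of √0.07 = 0.26.

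**2. What the planned model estimates.** Assume a true slope of 0, both variables with variance 1, and one factor identical within each pair that explains a share s of both variables in the same direction. Per pair:

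- Within pairs: W_xx = 1 − s and W_xy = 0, so the within-pair slope is 0.
- Between pairs: B_xx = 1 + s and B_xy = 2s, so the between-pair slope is 2s/(1 + s).
- The random-intercept slope is ω·B_xy/(W_xx + ω·B_xx), where ω is the within-pair residual variance divided by that variance plus twice the pair variance. To first order ω = (1 − s)/(1 + s).
- Substituting gives a spurious slope of about s/(1 + s). Ordinary regression that ignores pairs gives s.

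For s = 0.05, 0.10, 0.15 and 0.20 the spurious slope is about 0.05, 0.09, 0.13 and 0.17. Simulation of the REML fit gives 0.05 to 0.18, or roughly 20% to 70% of the 0.26 design effect. At s = 0.16 (correlation 0.4 with each variable) the simulated slopes are 0.158 ignoring pairs, 0.140 for the planned model and −0.002 within pairs. The pair effect therefore removes little of the bias.

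**3. False-positive rates.** Planned model, REML, 100 pairs, true slope 0, nominal 5%. Monte Carlo error is about one percentage point. The shares are assumptions, because the documents give none.

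| Share of each variable explained | One factor, same direction | Four independent factors, random directions |
|---|---|---|
| 0% | 5% | 5% |
| 5% | 10% | 6% |
| 10% | 25% | 11% |
| 15% | 49% | 16% |
| 20% | 72% | 22% |

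With the one factor in the model, rejection returns to 4% to 6%. With 50 pairs, the one-factor case gives 7%, 13%, 30% and 58% at correlations of 0.2, 0.3, 0.4 and 0.5 (shares of 4%, 9%, 16% and 25%).

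**4. Obese/lean status.** It is also absent from the Aim 2 model, and Aim 1 expects it to be related to SCFA. Suppose it correlates 0.3 with both responses. The planned model then rejects a true null in about 26% of runs. Adding only the matched covariates leaves this at about 26% to 30%; adding group restores about 5%. A within-pair slope without a group term does worse (spurious slope 0.166, rejection 37%), because every within-pair contrast is obese against lean.

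**5. Imperfect matching.** The plan gives no matching tolerance. If the factor correlates 0.8 rather than 1 within pairs, and 0.4 with each response, the within-pair slope is 0.044 with 7% rejection. Covariate adjustment gives 5%.

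**6. Cost.** Power for a partial R-square of 0.07 at n = 200 stays at 97.1% with 1 to 9 model terms.

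**The case against.** - **No evidence of confounding.** The documents report no association of age, sex, puberty or ethnicity with either response, and confounding needs both. Each response is a peak percent change, with SCFA taken relative to the subject's own fasting value, and eligibility is fairly narrow. These features may shrink the shares. This stands: the omission is certain, the harm is not.
- **The large rates are upper-end.** They need one factor, or several aligned factors, acting equally and in the same direction on both responses. This stands. A reader might infer from the 72% figure that the Aim 2 result would usually be spurious; the documents give no basis for that.
- **Aim 3 is a different design.** It is a crossover in obese subjects, so its covariate list does not show that Aim 2 contradicts the plan. This stands. The list shows only that the investigators regard these variables as usable covariates.
- **The no-adjustment sentence belongs to Aim 1.** A reader might infer that the plan expressly extends it to Aim 2. It does not say so. The point rests on the Aim 2 model as written, which lists one fixed effect.
- **Gender is not ignored.** An interaction model would normally carry a gender main effect. But that model is exploratory, names no other variable, and does not replace the main one.

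**Conclusion.** The point holds as a gap in the specification with a nearly free remedy. The planned Aim 2 slope mixes a within-pair part, which matching protects from the four factors so far as it is exact, and a between-pair part, which it does not protect. The direction and size of any bias are unknown. The false-positive rate runs from the nominal 5% if the factors explain nothing, through about 6% to 22% for four unaligned factors, to about 10% to 72% in the single-factor upper-end case. All these rates assume 100 pairs, exact matching, no group effect, and shares of 5% to 20% in both responses where the factors act at all.

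A reader might also infer that the four matched variables alone would put the slope right. They would not if obese/lean status is related to both responses, so the group term belongs in the same change.

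**What to change.** In the Aim 2 analysis paragraph of item 13, list age, sex, pubertal stage, ethnicity and obese/lean group as fixed effects beside peak percent total SCFA and the random pair effect.

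As a sensitivity analysis, split SCFA into the pair mean and the deviation from it, and report the within-pair slope with the group term kept in that model.

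The cost is two sentences. Age, sex, pubertal stage, ethnicity and group are already needed for enrolment and matching. Taking Tanner III to V as three levels and assuming three or four ethnicity categories, the added terms use 1 + 1 + 2 + (2 or 3) + 1 = 7 or 8 of about 200 − 2 = 198 degrees of freedom.

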Hypothesis: Lowering the amount of dietary CHO will shift the composition of the gut microbiota towards species with a lower ability to ferment carbohydrates and synthesize SCFA. Twenty-six obese subjects will be enrolled in a cross-over study and challenged with a low CHO or a normal CHO diet for a week. The subjects will switch diet after 4 weeks washout. Stool samples will be collected before and after the intervention to evaluate the gut microbiota. SCFA synthesis (as described in aim 1) will be measured at the beginning and at the end of the diet. Subjects will be enrolled after a 3 days run in period, in which they will try whether they could follow a low carbohydrates diet.

Dietary intervention.

a) Dietary Composition: The control “standard” diet composition will follow the American Dietary Guidelines of 55% CHO, 15% pro, and 30% fat. CHO content will be primarily complex CHO of high quality (14 g fiber/1,000 kcals and <10% of total kcals in the form of sugar). Fat content will be <7% saturated fats and primarily consist of monounsaturated fats. The experimental diet will consist of 30% CHO, 35% pro, and 35% fat. Since the experimental diet is lower in CHO, the fiber and sugar content will be calculated based on total CHO in the same percentage as the control (0.25 g fiber per each kcal of CHO and 18.2% sugar for total CHO). This will ensure the same quality of CHO in both diets (for example, <10% of total kcals from sugar would be a higher sugar intake in the low CHO diet). Kcal levels will be determined based on subject’s usual food intake. The subjects will be instructed to keep a 3-day food record (2 weekdays and 1 weekend day) prior to the study and the average kcal intake will be calculated using the Nutrition Data Systems for Research (NDSR) (University of Minnesota, 2016 version). Kcal levels will be assigned to the closest 200 kcals (1800, 2000, 2200, 2400, 2600, 2800, 3000). Utilizing the formulas to derive the same quality of CHO in both the standard- and low-CHO diets, the 2000 kcal standard diet, for example, will consist of 1100 kcals of CHO (55% total kcals), 27 g fiber (.025 g fiber per each kcal of CHO), and 50 g sugar (18.2% total CHO), while the low-CHO diet will consist of 600 kcals of CHO (30% total kcals), 15 g fiber (.025 g fiber per each kcal of CHO), and 27 g sugar (18.2% total CHO). A 3-day rotating menu will be

provided for both groups to ensure variety and increase compliance.

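### Aim 3 pre-tests treatment-by-period at p < 0.10 and, if significant, moves the primary diet comparison to first-period data; even without carryover the nominal 5% test then runs at about 7% or more.

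*Combined protocol and SAP*

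**What the plan says.** All of the analysis text is in the Combined protocol and SAP, Section I, item 13, Statistical Plan for Aim 3.

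- **Sizing:** "a two-sided 0.05 significance level a sample size of 21 obese children receiving both low CHO vs control diet will be required", for a difference of 0.75 with SD 1.0 and 90% power. Enrolment is 26, to allow for dropout.
- **Outcome:** "follow-up peak total SCFA minus the baseline peak total SCFA divided by the baseline peak total SCFA", compared between diets in a mixed model with diet, period, a random subject effect and "baseline covariates of SCFA, age, sex, pubertal stage and ethnicity".
- **Switch:** "The treatment by period interaction will be evaluated and if significant" at p < 0.10, "examination of the primary aim will focus on the interventions received during the first period". The stated reason is to rule out carryover.
- **Estimation:** "Linear contrasts and two-sided 95% confidence intervals will be estimated comparing mean percent peak total SCFA change for low CHO to control". No separate level or interval is given for the first-period branch.

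The design text is in Section I, item 4, Aim 3. It says "SCFA synthesis (as described in aim 1) will be measured at the beginning and at the end of the diet" and "The subjects will switch diet after 4 weeks washout". Under c) Instruction of Isocaloric Diets, the washout label is attached instead to the four weeks after the run-in. The calendar of activities at the end of item 4 lists the four Aim 3 visits in weeks 4, 5, 6 and 7.

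**The concern.** With two sequences and two periods, treatment-by-period is aliased with sequence. It is tested by comparing subjects' two-period totals between sequences. Those totals contain the first-period values, so the pre-test and the first-period test share data. Once the pre-test has come out significant, the first-period test is no longer a 5% test, and its interval no longer covers 95% of the time.

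The switch also moves the answer from a within-subject comparison, for which 21 was sized, to a between-subject comparison of about 11 against 10. The plan's verb, to focus, does not settle whether the two-period result is still reported or which result counts as primary.

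At stake are the error rate and coverage of the randomised diet comparison. The rule is also the only analysis step that the plan offers as protection against carryover, and the washout behind it is not described consistently.

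**Working it through.** **Inputs.** From the Statistical Plan for Aim 3: pre-test level 0.10, final level 0.05 two-sided, difference 0.75, SD 1.0, 21 evaluable and 26 enrolled. Item 4, Aim 3, b) Run-in period randomises which diet comes first but gives no ratio; 1:1 is assumed (11/10 or 13/13). The between-period correlation rho is not given and is varied. The random subject effect implies rho of at least 0, but negative values were also tried. The first-period result is taken to replace the two-period result when the switch fires.

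**Step 1: the plan's own figure.** For a paired t-test with SD of the within-subject difference 1.0, the noncentrality is 0.75 × √n. Power is 0.8888 at n = 20 and 0.9045 at n = 21, so 21 reproduces.

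**Step 2: dependence.** Let Y1 and Y2 have common variance σ² and correlation rho.

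- Pre-test (Y1 + Y2) against first period (Y1): σ²(1 + rho) / √[2σ²(1 + rho) × σ²] = √((1 + rho)/2). This is 0.71 at rho 0 and 0.87 at rho 0.5.
- Pre-test against two-period contrast (Y1 − Y2): covariance 0, so the two are independent.

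**Step 3: type I error with no carryover.**

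Overall level = (1 − 0.10) × 0.05 + P(|Z_pre| > 1.645 and |Z_first| > 1.960)

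- rho 0: 0.045 + 0.10 × 0.2506 = 0.0701
- rho 0.5: 0.045 + 0.10 × 0.3703 = 0.0820
- rho 0.9: 0.045 + 0.10 × 0.4872 = 0.0937
- limit at rho 1: 0.045 + 0.10 × 0.50 = 0.0950

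Simulation with t-tests, 100,000 trials per cell:

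| rho | Rule, N = 21 | Rule, N = 26 | Two-period test, N = 21 | First-period test once switched, N = 21 |
|---|---|---|---|---|
| 0 | 6.9% | 6.8% | 4.9% | 24% |
| 0.25 | 7.5% | 7.5% | 5.0% | 29% |
| 0.5 | 8.1% | 8.3% | 5.1% | 36% |
| 0.75 | 8.9% | 8.8% | 5.1% | 44% |
| 0.9 | 9.4% | 9.3% | 5.0% | 49% |

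Negative correlation lowers the figure but does not restore 5%: simulation gives 6.4% at rho −0.25 and 6.0% at −0.5. Coverage of the nominal 95% interval is 91-93% for rho 0 to 0.9. If SD 1.0 were both the per-period SD and the SD of the difference, then 2(1 − rho) = 1, so rho = 0.5 and the error is about 8%.

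**Step 4: power for 0.75, N = 21, SD of difference 1.0.** The two-period test has about 90%. The rule at rho 0 has about 0.90 × 0.90 + 0.10 × 0.56 = 0.87; simulation gives 86-87% for rho 0 to 0.75. Once switched, power is roughly half (49-56%).

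The first-period comparison on its own, 11 v 10, has 37% power if SD 1.0 is per period. It has 63% if 1.0 is the SD of the difference and rho is 0 (per-period SD 1/√2 = 0.71). For 13 v 13 the figures are 45% and 74%.

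**Step 5: closer to the planned model (illustrative).** This used percent change from each period's own baseline, REML with the planned covariates, and log-normal data with assumed error SD 10% or 30% and subject SD 30%. At rho 0 the rule gives 6.6-7.2%, against 4.8-5.5% for the two-period test. With rho about 0.25-0.75 it gives 6.9-8.2%, against 3.9-5.1%. Coverage is 92-93%. The distributional inputs are not in the documents, and the conclusion does not depend on this step.

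**The case against.** The strongest reply is that the rule buys protection if carryover is real, at a price of about 2 false positives per 100. In the simplified model (N = 21, SD of difference 1.0), an always-two-period estimate is biased by half the carryover, and the comparison is:

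| Carryover, rho | Bias toward zero, rule v two-period | RMSE | Coverage | Power |
|---|---|---|---|---|
| 0.375, rho 0 to 0.5 | 0.09-0.10 v 0.19 | 0.31-0.37 v 0.29 | 86-87% v 87% | 71-74% v 69% |
| 0.75, rho 0 | 0.10 v 0.37 | 0.38 v 0.43 | 79% v 63% | 62% v 37% |
| 0.75, rho 0.5 | 0.17 v 0.38 | 0.47 v 0.43 | 69% v 63% | 49% v 37% |

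This stands. If carryover is as large as the diet effect, the rule does better on most measures, though it does not restore 95% coverage either. At half that size the two approaches are close.

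Other points have some force:

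- Percent change from each period's own baseline gives some protection: a half-size residual effect on both the period-2 baseline and follow-up largely cancels (bias 0.02, or 0.09 with 30% error). On the follow-up alone it biases the two-period estimate 0.19 toward zero; on the baseline alone, 0.19 away from zero. The rule leaves about 0.11 in each of those two cases. So the protection depends on where the residual effect falls.
- The two washout statements in the text can both be true, since the run-in is itself a low-carbohydrate diet. But read literally, the calendar's consecutive weeks leave no four-week gap, so reconciliation is still needed.
- Subjects lost after period 1 still contribute first-period data, so that set could be as large as 13 v 13. That raises its power but does not change the type I error.
- The rule is prespecified. That prevents an ad hoc choice of threshold but does not correct the level.

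**Conclusion.** The concern holds. Followed as written, and with no carryover at all, the Aim 3 primary comparison runs at about 7% if rho is 0 and up to 9.5% as rho approaches 1, against a stated two-sided 5%. Its 95% intervals cover 91-93%. Power drops by about 3 to 4 points with 21 subjects. The effect is modest because without carryover the switch fires in only about 7-11% of trials. When it does fire, the nominal 5% first-period test falsely rejects in about a quarter of null trials at rho 0, and in up to half at high rho.

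The figures assume 1:1 sequences, equal variances in the two periods, and first-period results replacing the two-period result. The value of rho is unknown, but no value examined from −0.5 upward brings the error back to 5%. This should be fixed; it does not invalidate the design.

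**What to change.** Delete the conditional switch. State that the two-period mixed model (diet, period, random subject, planned covariates) is the primary analysis whatever the interaction p-value. Report as sensitivity analyses:

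1. the treatment-by-period estimate with its confidence interval;
2. the first-period diet contrast;
3. the change in pre-diet SCFA from period 1 to period 2, compared between sequences. These measurements are already planned, and this shows whether a residual effect has reached the period-2 baseline, where the direction of bias would reverse.

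At the same time, reconcile the three descriptions of timing in item 4 (washout between diets, washout after the run-in, and the calendar weeks). Add a sentence on why the interval between diets is thought sufficient, because the no-carryover assumption will rest on it. If doubt remains, fix the choice of primary analysis in advance on design grounds, not on the interaction p-value.

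Keeping the switch at a corrected level is possible but unattractive. The first-period test would need a level of about 0.005-0.007 to hold the total at 5%, and its power at 0.05 is already low.

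The cost is SAP wording and a short washout justification, with no new data or subjects. The downside is that, if carryover is real, the primary estimate is biased by an amount that the sensitivity analyses can reveal but not remove.
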